Credibility/Expectancy Questionnaire (CEQ)⁹⁶: This 6-item self-report questionnaire has two subscales: (1) treatment rationale credibility (CEQ-C) is cognitively based (e.g., “How logical does the therapy offered to you seem?”), and (2) treatment expectancy (CEQ-E) is emotionally based (e.g., “How much do you really feel that therapy will help you to reduce your symptoms?”). The CEQ will be administered at the baseline clinical assessment visit (week 0) as well as at the start of session 3.

Client Satisfaction Questionnaire (CSQ-8)^{97,98}: This 8-item self-report questionnaire assesses satisfaction with clinical services received. The CSQ will be administered at the post-treatment clinical assessment visit (week 8).

Working Alliance Inventory (WAI-SR)⁹⁹: The WAI-SR is based on Bordin’s (1979) conceptualization of therapeutic alliance¹⁰⁰ which includes three factors: (1) bond alliance (e.g.,

“___ and I respect each other”), (2) goal alliance (e.g., “___ and I are working towards mutually agreed upon goals”), and (3) task alliance (e.g., “___ and I agree on what is important for me to work on”). Compared to the original 36-item WAI, the revised short version (WAI-SR) has an improved model fit in confirmatory factor analyses¹⁰¹.

Homework Compliance: Therapists and patients are asked to rate the amount of between-session homework participants completed on a scale from 1 (patient did not attempt the assigned homework) to 5 (patient did more of the assigned homework or its equivalent than was requested). Therapists and patients also rate effort made by the patient in completing the assignment on a scale from 0 (patient made no attempt to complete any homework) to 4 (patient made maximal efforts to complete homework). Finally, therapists rate the relevance of the homework attempted to the patient’s particular problem on a scale from 0 (homework attempted was completely unrelated or not done) to 4 (homework attempted relevant to particular target problems). These measures have been used in previous studies of ERT³¹ and will be administered weekly at the therapy sessions.

Adherence and Competence^{31,102}: For supportive psychotherapy, manual adherence on a scale from 1 (not at all) to 7 (completely) and competent treatment delivery on a scale from 1 (not at all) to 5 (completely) will be rated to ensure minimum scores of ≥ 6 on adherence and ≥ 4 on competence for selected sessions (as described below under “Monitoring and Quality Assurance”). For attention regulation therapy, manual adherence will be rated on a scale from 0 (did not address component/engage action) to 2 (addressed component/engaged action in more detail), and competent treatment delivery will be rated on a scale from 0 (therapist was not skillful or performed poorly) to 2 (therapist performed action very skillfully). The specific skills to be rated on this measure were developed during the study and submitted as an IRB amendment.

Blinding Questionnaire: This measure will be completed by the IE at 3-month follow-up in order to assess whether they believe the participant has been assigned to AR-ERT or SPT and how strongly they believe this (i.e., somewhat or strongly).

Other Assessments

The **Lifetime Medication History** self-report form reviews lifetime medication treatment (i.e., prior to past 2 months).

Intolerance of Uncertainty Scale (IUS-12)¹⁰³: The IUS-12 is a self-report measure capturing reactions to uncertainty, ambiguity, and the future and consists of two subscales: (a) *Prospective IU* measures discomfort due to future unknowns and information gathering to increase certainty (e.g., “I always want to know what the future has in store for me”), and (b) *Inhibitory IU* measures avoidance and paralysis in the face of uncertainty (e.g., “When I am uncertain I can’t function very well”). The IUS-12 will be administered at the clinical assessment visits (baseline, mid-treatment, post-treatment, and 3-month follow-up).

Health Behaviors Questionnaire: This measure will be administered at the computer task visits (baseline, mid-treatment, post-treatment) in order to assess health-related behaviors participants may have engaged in over the past 24 hours that would affect interpretation of the physiological readings.

Post-EEG Questionnaire: This questionnaire probes whether participants were uncomfortable, anxious, sleepy, or inattentive during the EEG recording and will be administered directly after each EEG session (baseline, mid-treatment, post-treatment).

COVID-19 Impact Scale: This 14-item self-report measure was created by members of the Center for OCD and Related Disorders and aims to assess the effect of the coronavirus pandemic on individuals in the past week. Individuals are instructed to rate the extent to which they agree/disagree with various statements (e.g., “I found it difficult to tolerate the uncertainty about whether I or a loved one would contract COVID-19”) on a scale from 1 (Strongly Disagree) to 5 (Strongly Agree). The COVID-19 Impact Scale will be administered at the clinical assessment visits (baseline, mid-treatment, post-treatment, and 3-month follow-up).

Experiences Questionnaire - Decentering (EQ-D)¹⁰⁴: In this 11-item subscale, individuals are asked to indicate how often they currently have various decentering experiences (e.g., “I am consciously aware of a sense of my body as a whole”) on a scale from 1 (Never) to 5 (All the time). The EQ-D will be administered at baseline, mid-treatment, post-treatment, and 3-month follow-up.

Emotion Regulation Questionnaire (ERQ)¹⁰⁵: The ERQ is a 10-item self-report measure of emotion regulation that includes statements related to *cognitive reappraisal* (e.g., “When I’m faced with a stressful situation, I make myself *think about it* in a way that helps me stay calm”) as well as *expressive suppression* (e.g., “I control my emotions by *not expressing them*”). Individuals are asked to rate the extent to which they disagree/agree with these statements on a scale from 1 (Strongly disagree) to 7 (Strongly agree). The ERQ will be administered at baseline, mid-treatment, post-treatment, and 3-month follow-up.

Emotional Attentional Control Scale (eACS)¹⁰⁶: This 14-item self-report measure, which was adapted from the original 20-item Attentional Control Scale (ACS), assesses modulation of attentional control in emotional contexts. Individuals rate each item on a 4-point scale from 0 (almost never) to 4 (always). The eACS will be administered at baseline, mid-treatment, post-treatment, and 3-month follow-up.

Treatment Preference Form: This self-report form aims to capture the degree to which each participant prefers a given treatment condition (AR-ERT or SPT) before they are randomized. Participants are made aware that this form will have no bearing on treatment assignment and will not be viewed until after the participant has completed treatment.

Patient Feedback Questionnaire: This questionnaire allows participants to provide feedback on their experience during treatment, including general satisfaction with their treatment condition and treatment length, which aspects of therapy they found most confusing or most helpful, and usefulness of the therapy website and forms. This self-report questionnaire will be administered at post-treatment only.

After ART Usage and Additional Treatment Form: This self-report form asks participants to report their usage and the usefulness of the study website, and probes for the need for additional treatment at the 3-month follow up assessment.

Equipment

Eye-tracking data will be collected during the AEDT and EIT tasks. The eye tracking equipment will be located in a dedicated office within the OCD Program. We will use a Tobii Pro X3-120 screen-based eye tracker (The Tobii Group, Danderyd, Sweden) which samples eye-

gaze coordinates at 120 Hz. Eye tracking data will be transmitted via USB 3.0 to a LAN with External Processing Unit and converted to visual fixation data using the iMotions Biometric Research Platform (Boston, MA, USA).

The electroencephalogram (EEG) equipment is located at the MGH Martinos Center (Charlestown, MA). EEG data will be acquired using BrainVision software (Brain Products GmbH, Gilching, Germany) that is installed in a dedicated behavioral testing laboratory. The EEG amplifier is an actiCHamp active amplification system (24-bit battery, up to 1000 Hz sampling rate). It is used with actiCAP EEG caps, which are fitted with 32-electrode modules. Our system is configured for use with 96 electrodes (3 modules) to provide dense scalp coverage, which is helpful for spatially localizing event related potentials (ERPs) and is necessary for accurate source localization. The cap can be fit to a participant in about 30 minutes to provide an individualized and comfortable fit for each person. The actiCHamp system uses active electrodes and gel to minimize impedance and maximize signal-to-noise ratio (SNR); impedances will be kept under 30 kOhms to ensure high SNR. The N2 and N450 ERP components will be measured at midline frontal (Fz) and central (Cz) sites, while the P300 will be measured at a midline parietal site (Pz). Digitization of three-dimensional electrode positions will be accomplished via the BrainVision CapTrak system. Data processing and analysis will occur offline using BrainVision Analyzer 2.0 and MatLab (Natick, MA, USA).

Randomization

At the baseline visit, eligible subjects will be randomized (1:1 in parallel) to AR-ERT or SPT using the REDCapTM database.

Treatment

For all participants, treatment will consist of 8 weekly sessions provided via Healthcare Secure ZoomTM that are 60 minutes in duration. Eight sessions is the length of ERT currently being tested,^{107,108} allowing us to directly compare our effect sizes with the full package. All sessions are individual treatment (no group treatment).

Attention Regulation – Emotion Regulation Therapy (AR-ERT)

A brief, manualized version of individual Emotion Regulation Therapy (ERT) focused on the Attention Regulation module will be administered to patients randomized to AR-ERT. Specifically, the 8-session protocol will be a streamlined version of ERT, which tested as part of a NIH-sponsored R34:MH070682. The full protocol^a engages several active mechanisms (i.e., attention regulation, metacognitive regulation, reward/threat processing) and an 8-session version of this full treatment is currently being studied; however, in order to test the target of attentional/cognitive control, we are focusing solely on attention regulation skills: (a) Orienting (i.e., the ability to flexibly shift attention) via mindfulness of the breath (sessions 1-4), and (b) Allowing (i.e., the ability to sustain attention despite unpleasant emotional experiences) via mindfulness of thoughts and emotions (sessions 5-8). Treatment will also include lessons for practicing these skills in two different contexts: (a) reactive: reviewing challenging (i.e., emotion-laden) situations that have happened in the past week in which attention regulation skills could have been applied to counter automatic reactive RNT responses (sessions 1-4) as well as (b) proactive: preparing for challenging situations that may happen in the future in which skills could be implemented (sessions 5-8).

Specifically, session 1 provides patients with a model of how RNT maintains emotions, presents between-session self-monitoring of RNT, and introduces the attention regulation skill of Orienting via mindfulness of the breath. In sessions 2-4, Orienting skills continue to be practiced. Patients review their self-monitoring forms to detect triggers and consequences of RNT. They also conduct in-session imaginal rehearsal of situations from the past week that

didn't go as planned in order to explore effective alternatives (i.e., earlier cue detection of RNT; how attention regulation skills could have been applied to counteract RNT). Session 5 begins the second half of treatment, in which the skill of Allowing is introduced via mindfulness of thoughts and emotions. In addition, proactive strategies are taught to prepare for emotion-laden situations that trigger RNT that patients may be avoiding, have withdrawn from, or that RNT prevents them from fully experiencing. Specifically, session 5 includes in-session imaginal rehearsal of upcoming situations that the patient wants to engage in, including confronting imagined difficulties and feared outcomes. In sessions 6-7, Allowing will continue to be practiced. Proactive imagery exercises also continue and additionally involve *in vivo* proactive exercises to approach situations that typically trigger RNT. Finally, session 8 includes a summary of patients' gains, relapse prevention, and processing of termination. Home practice assignments are assigned after each session. Materials needed to complete between-session assignments will be emailed to participants using REDCap as well as housed on a website (<https://mghocd.org/art/>). This website will not store any data; instead, it will simply host links to various materials (e.g., links to PDFs for them to download, links to pre-recorded session recap videos summarizing the skills associated with that session, and links to REDCap surveys). The website (hosted by Wordpress) will require a passcode to enter ("attention"), which will only be shared with participants receiving Attention Regulation - Emotion Regulation Therapy.

Supportive Psychotherapy (SPT)

To control for nonspecific therapy elements (e.g., expectancies, demand characteristics), half of participants will be randomized to SPT.^{109–113} SPT is one of the most common psychological therapies provided in the community for affective disorders,¹¹⁴ and thus is a credible control condition (which will minimize attrition), yet it is not hypothesized to engage the target of attentional/cognitive control. SPT is also acceptable from a safety perspective, as it allows close patient monitoring. Manualized SPT has been used as the control condition in other NIH-funded studies in our program.

SPT focuses on therapeutic interactions and techniques that are nonspecific and common to psychotherapies (e.g., reflective listening, expression of empathy), and sessions are non-directive and conversational, with content driven by the patient.¹¹⁵ SPT focuses on maintaining, improving, and restoring self-esteem and adaptive coping skills, and on reflecting and expressing emotions about current life issues. The intent is to help patients learn to cope with external and internal (psychological) challenges.^{115–117} SPT emphasizes the therapeutic relationship and self-esteem as vehicles for patient improvement.^{115,116} Session content may include discussion of relationships and emotions (related and unrelated to RNT symptoms). SPT therapists take an empathic and validating stance so that patients are comforted when upset and supported when coping with distressing feelings. Specific SPT techniques include communicating positive regard for the patient through verbal and nonverbal behavior; using a relaxed conversational style in the therapy; providing empathy, praise, and encouragement; clarification; ventilation (allowing the patient to express intense feelings); and absolution (i.e., normalizing minor inadequacies to eliminate guilt).

Adjunctive Services and Attrition Prevention (ASAP)

In addition to the scheduled AR-ERT and SPT sessions, each participant will be permitted up to two ASAP sessions. An ASAP session addresses subject crises or unusual circumstances/needs that may arise, with the goal of subject retention. This strategy has been implemented successfully in other large federally funded randomized controlled trials in our clinic.

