5. STUDY PROCEDURES

Overview

This is a single-site study at the MGH Richard B. Simches Research Center (Boston, MA) and Athinoula A. Martinos Center for Biomedical Imaging (Charlestown, MA). Eligible participants will complete: (1) 3 electroencephalogram (EEG) sessions which record brain activity while participants sit at rest (i.e., resting state functional connectivity) and perform a computer task (2 hours), (2) 3 computer task sessions in which participants view a series of images (i.e., faces, scenes), and we measure where on the screen they are looking using an eye tracker and the sweatiness of their palms (60-90 min), (3) an 8-week therapy protocol (60 minutes each) – with random assignment to either Attention Regulation – Emotion Regulation Therapy (AR-ERT) or supportive psychotherapy (SPT), and (4) 4 clinical assessment visits including clinician interviews and self-report measures at baseline (week 0), mid-treatment (week 4), post-treatment visit (week 8), and 3-month follow-up (week 20). The EEG sessions will take place at the Martinos Center and the computer task sessions will take place at the MGH Center for OCD and Related Disorders in Simches. Clinical assessments will take place virtually using Healthcare Secure Zoom™, an encrypted and HIPAA-compliant video conferencing platform (or over the phone). Treatment visits will also take place virtually and will be conducted using Healthcare Secure Zoom™ (or over the phone). Twenty-four hours prior to EEG and computer task sessions, participants will be screened for COVID-19 symptoms by completing the MGB COVID-19 Prescreen Questions. Subjects will be given the option of combining the screening and baseline clinical assessment visits (if they are deemed eligible for the study after screening) and combining the mid-treatment and post-treatment clinical assessment visits to their treatment session visits (to reduce subject burden). Thus, study participation may only involve 16 total visits if such visits are combined. To avoid dropout, subjects will be paid \$20 each for the baseline, mid-treatment, post-treatment, and 3-month follow-up clinical assessments, \$20 each for the 3 EEG sessions, and \$20 each for the 3 computer task visits (\$200 total). Participants who cannot afford to travel to the treatment facility will be provided with transportation fare (e.g., parking passes) to attend in-person study visits (\$12.50 x 3 computer task visits at the Simches Building + \$7 x 3 EEG sessions at the Martinos Center = \$58.50).

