Emotional Interference Task (EIT)⁷⁰: The EIT measures difficulties *sustaining attention* in the presence of distressing emotional contexts. Participants view 40 neutral and 40 arousing (20 pleasant and 20 unpleasant) photographs from the International Affective Picture System (IAPS)⁷¹ for 6 seconds each, in random order, with a 1-second interval between pictures (148 trials). A high- or low-pitched tone is played either 1 or 4 seconds after each picture is presented, and participants are instructed to choose whether each tone is high or low by pressing a button as quickly as possible after each tone is played. Mean reaction times are calculated separately for pleasant, unpleasant, and neutral pictures. Emotional interference is then calculated separately for pleasant and unpleasant stimuli by subtracting mean reaction times recorded while viewing neutral pictures from mean reaction times recorded while viewing pleasant and unpleasant pictures. Faster reaction times reflect better ability to inhibit emotional interference while sustaining attention on the tone; we will also collect gaze data to validate for future research. Past research has indicated that patients with GAD demonstrate slower reaction times on the EIT vs. controls, and symptom improvement is associated with faster reaction times.^{43,72} The EIT will be administered at the following timepoints: baseline (week 0), mid-treatment (week 4), and post-treatment (week 8). Computer task sessions will occur within a 7-10-day window, but no longer than 14 days, from each clinical assessment visit.

Psychophysiological Measurement. Galvanic Skin Response (GSR) will also be measured during the EIT at baseline, mid-treatment, and post-treatment. Biometric measurement of this psychophysiological index will be recorded using the iMotions platform.

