Concomitant Therapy (CTHER) Log: The RA will administer the CHER form at the clinical assessment visits (baseline, mid-treatment, post-treatment, and 3-month follow-up) and before each therapy session to probe for any changes in therapy that may have occurred since the last session. Changes in therapy are not allowed during the study. At each visit, the research coordinator will ask the subject whether they have started or stopped any mental health treatments such as counseling, therapy, or self-help programs to ensure that this does not occur without our knowledge. The therapist reviews the completed CHER Log before each therapy session.

Life Events Questionnaire: This form is administered by the RA and reviewed by the PI at the clinical assessment visits (baseline, mid-treatment, post-treatment, and 3-month follow-up) to assess whether any major life events occurred since the last assessment visit that might have had a psychological impact on the participant including: marriage, divorce or separation from spouse, death of a spouse/partner or other close family member, birth of a child, serious injury, diagnosis/progression of a medical illness or disease (e.g., COVID-19 exposure or diagnosis), loss/began new job.

Adverse Events (AE) Form and Log: The AE Form will be administered by the RA during clinical assessment visits (baseline, mid-treatment, post-treatment, and 3-month follow-up) and by the therapist during treatment sessions to probe for any adverse events. Should the participant report an adverse event, the RA or therapist will log this information in the AE log while speaking to the participant. If there are any safety concerns during a clinical assessment, the RA will inform the IE of the adverse event. The RA and therapist will document any adverse events that occur during the study and the PI will review each event during weekly study meetings to discuss relatedness to treatment, severity, and corrective actions. We have used these forms in prior NIH-funded psychotherapy studies.

Assessment of Treatment Credibility and Satisfaction:

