6. BIOSTATISTICAL ANALYSIS

Overview

Data acquisition and analytics approaches will be performed by [name] under the supervision of biostatistician [name]. To characterize our sample, data will be displayed graphically, and summary statistics (e.g., means and frequencies) will be calculated for all variables, including demographic and clinical descriptors. Descriptive statistics and exploratory graphing (e.g., scatter plots) will be used to assess normality, skew, and outliers on all measures. Continuous measures will be transformed if necessary, to satisfy assumptions of normality and homogeneity of variance.

Baseline differences between the treatment arms (AR-ERT vs. SPT) in demographic and other potential prognostic variables will be examined using chi-square analyses for discrete variables and ANOVA for continuous variables. While randomization tends to produce well-balanced treatment samples, if we find significant differences in potentially important baseline variables, we will include these variables as covariates in subsequent multivariate analyses. Candidate covariates for adjustment include baseline values of RNT (PTQ-PW score), symptom measures (Y-BOCS, SIGH-A, SIGH-D), and use of psychotropic medication (yes/no). Additional covariates that are unlikely to moderate treatment effect, but nonetheless will be examined for completeness, include: age, gender, education, race/ethnicity (majority vs. minority as we do not anticipate recruiting enough subjects from any one minority group to perform analyses for specific groups). If effects of gender and/or minority status are found that might be clinically meaningful, even if not statistically significant, we will report these to guide future research. Frequencies of adverse events (with 95% confidence intervals) will be calculated by treatment arm and type of event. We also will compare treatment groups on baseline credibility/expectancy of treatment and post-treatment satisfaction. A two-tailed p value $<.05$ will be considered evidence of statistical significance for the primary outcome.

Missing Data

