- c) As part of the informed consent process, participants will be asked if they are willing to provide contact information for two friends or family members and to give permission to have the research team call or write to these individuals in the case of an emergency (i.e., if we have concerns about their wellbeing).
 - d) Suicidality will be closely monitored with the BDI-II suicide item (#9) and clinician inquiry at each visit.
 - e) Patients at higher risk will be withdrawn from the study as described in the next section below.
 - f) [name] (or covering clinician in her absence) will be available 24/7 to participants in the event of a clinical emergency; this will be clearly communicated orally and in writing to study participants (i.e., the consent form describes how to reach the investigators in an emergency). Participants will be referred for a higher level of care as needed.
 - g) In the event that a study staff member witnesses behaviors such as abuse or neglect of children or the elderly while conducting a virtual study visit via Zoom™, they will report this to the PI who will consult with the Office of General Council and follow hospital policy for reporting such behaviors.
- 7) **Participant Withdrawal.** Subjects may be withdrawn from the study for *any* of the following reasons:
- a) A significantly deteriorating clinical course, such as emergence of active suicidal ideation or a need for hospitalization.
 - b) Score of ≥ 2 on the BDI-II suicide item (#9) and subsequent evaluation by the PI indicating it would be unsafe for the patient to remain in the study.
 - c) Score of 6 (much worse) or 7 (very much worse) on the CGI-I for 3 consecutive weeks and therapist and PI judgment that remaining in the study is not in the subject's best interest; a patient may be withdrawn sooner than this, if in the judgment of the therapist and PI, this is in the patient's best interest.
 - d) PIs' decision that withdrawal from the study is in the subject's best interest.
 - e) Subject's decision to withdraw.

Subjects who require medication changes or begin other types of therapy (e.g., family therapy) will be kept in the study even though such events violate study procedures. We will compare outcome data for compliant and non-compliant subjects.

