1. Becoming tired or uncomfortable answering assessments and questionnaires
2. Discomfort from scraping skin on the scalp during EEG procedures
3. Distress from the computerized images during the eye-tracking task
4. Temporary increase in anxiety or depression during treatment
5. Possible loss of privacy (e.g., due to contacting an emergency-contact or due to legal limits of confidentiality)

An IRB approved AE Tracking log will be administered by the RA and reviewed by the PI at the clinical assessment visits (baseline, mid-treatment, post-treatment, and 3-month follow-up) to probe for any adverse events that occurred since the last visit.

Adverse events and Unanticipated problems will be reported to the MGB IRB in accordance with its policy. Specifically, in accordance with guidelines of the Office for Human Research Protections (OHRP) and NIMH, reporting of adverse events will occur to (1) the MGH IRB, (2) the NIMH program officer, (3) OHRP, and (4) the DSMB as follows:

- 1) Unexpected **serious adverse events** (SAE) related to study participation (e.g., death, life threatening AE, suicide attempt, inpatient hospitalization) will be reported within **5 business days** of the study team first learning of a death and within **10 business days** of the study team becoming aware of a non-death SAE.
- 2) Any **other unanticipated problems** involving risks to subjects or others will be reported within **10 business days** of the study team becoming aware of the event.
- 3) All **adverse events** and SAEs that are deemed expected or unrelated to the study will be summarized in **twice-annual progress reports** for the DSMB and in **annual progress reports** for the NIMH and IRB.

Documentation to be submitted for reportable events will include:

- Identifying information for the research protocol (e.g., project title, investigator's name, and the grant/contract number)
- The date on which the event occurred and the date at which the PI became aware of the event
- A detailed description of the event and impact on the participant(s)
- A detailed description of the measures taken (including clinical) in response to the event (if any)
- Confirmation that the appropriate monitoring entities and regulatory bodies have been notified as needed
- A description of any changes to the protocol or other corrective actions that have been taken or are proposed in response to the event

Data Management

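### No adverse-event question is scheduled at the computer-task and EEG visits, so procedure-related events, image distress above all, risk being under-ascertained

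*Combined protocol and SAP*

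**What the plan says.** Section 5 (Adverse Events Form and Log) states that the form is "administered by the RA during clinical assessment visits (baseline, mid-treatment, post-treatment, and 3-month follow-up) and by the therapist during treatment sessions". The AE row of Table 1 agrees: baseline, weekly, post-treatment and 3-month follow-up, given by the RA or therapist.

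The Section 5 overview lists, apart from therapy and clinical assessments, "3 electroencephalogram (EEG) sessions which record brain activity while participants sit at rest" and "3 computer task sessions in which participants view a series of images". For timing, "Computer task sessions will occur within a 7-10-day window, but no longer than 14 days, from each clinical assessment visit"; the EEG sessions have the same window. Neither statement says whether the session comes before or after the assessment.

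Section 9 (Adverse Events Reporting) lists five expected events. Item 2 is discomfort from scraping the scalp for EEG. Item 3 is "Distress from the computerized images during the eye-tracking task". Section 7 explains that some of the pictures are violent, gory or sexual and may distress participants.

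Section 6 (Overview) commits to an analysis: "Frequencies of adverse events (with 95% confidence intervals) will be calculated by treatment arm and type of event".

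On suicidality, Section 7 (Emergencies and Suicidality, item d) says: "Suicidality will be closely monitored with the BDI-II suicide item (#9) and clinician inquiry at each visit".

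**The concern.** Two of the five events that the protocol itself expects belong to visits at which no AE question is scheduled. Image distress is the sharper case. The participants were selected for perseverative thinking, and the protocol takes the risk seriously enough to show sample pictures in advance. Yet no instrument asks about distress on the day of the computer task. The Health Behaviors Questionnaire given there covers behaviour over the previous 24 hours that could affect the physiological readings.

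At stake is the AE table by event type. Events that are not asked about when they happen are recorded only if the participant volunteers them, the RA notices them, or they are recalled at a later probe. Transient distress is the kind of event most easily lost in that way.

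**Working it through.** **1. Are these separate visits?** The overview gives a minimum of 16 visits when visits are combined. That figure reproduces only if the six sessions count separately: 1 (screening with baseline) + 8 (therapy, with mid- and post-treatment assessments attached) + 1 (follow-up) + 3 (EEG) + 3 (computer task) = 16. So 6/16 = 37.5% of visits have no scheduled AE Form. With nothing combined the total is 8 + 4 + 1 + 3 + 3 = 19, and the share is 6/19 = 31.6%.

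**2. What is asked at each kind of visit?**

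| Visit | AE Form scheduled | Other same-day question on discomfort or distress |
|---|---|---|
| Clinical assessment (4) | Yes, RA | – |
| Therapy session (8) | Yes, therapist | – |
| EEG (3) | No | Post-EEG Questionnaire, not linked to the AE log |
| Computer task (3) | No | None described |

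**3. How long until the next AE Form?** After the baseline and mid-treatment sessions, a weekly therapy session normally follows, so the wait is about a week. For the post-treatment session, take week 8 as day 56 and week 20 as day 140.

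- Session *d* days before the week 8 assessment: wait = *d*, at most 14 days.
- Session *d* days after it, with therapy ended: wait = 140 − (56 + *d*). This gives 84 days for *d* = 0, 77 for *d* = 7, 74 for *d* = 10 and 70 for *d* = 14, which is 10 to 12 weeks.

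**4. What could this do to the frequencies?** The documents give no event rates or capture rates, so the following is illustration only. Assume a probability *p* of an event at each of three sessions, independent between sessions, full capture at the first two, and capture fraction *c* at the last. The true share of participants with any event is 1 − (1 − *p*)³. The recorded share is 1 − (1 − *p*)²(1 − *pc*).

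| *p* | True share | Recorded, *c* = 0 | Recorded, *c* = 0.5 | Recorded/true, *c* = 0 | Recorded/true, *c* = 0.5 |
|---|---|---|---|---|---|
| 0.05 | 0.143 | 0.098 | 0.120 | 0.68 | 0.84 |
| 0.30 | 0.657 | 0.510 | 0.584 | 0.78 | 0.89 |

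With complete recall (*c* = 1) the ratio is 1. The result depends almost wholly on *c*, about which the documents are silent.

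**5. Suicidality wording.** Table 1 lists the BDI-II suicide item at screening and weekly, and the full BDI-II at the four clinical assessments. It schedules no suicide item for the six task visits, although Section 7 refers to every visit.

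**The case against.** A good deal can be said for the plan.

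- **The log looks back.** Section 9 has it cover the time since the last visit, and Section 5 makes the RA and therapist responsible for documenting any event during the study. Table 1 has the RA running these tasks. A reader might infer that the AE frequencies will be too low. The documents do not show that; they support only a risk. What remains is that, without a scheduled question, capture rests on volunteering, observation or recall.
- **There are same-day safeguards.** The Post-EEG Questionnaire covers three of the six visits. Staff check comfort while EEG sensors are placed, participants may stop the EEG, decline the picture task or look away, and a clinician is reachable at all hours. It would be wrong to say that nothing would signal distress on the day. But most of these measures prevent or manage distress; they do not record it for the AE analysis.
- **The long gap is conditional.** It concerns only the last time point, and only if the session follows the week 8 assessment and the end of therapy. That stands. The protocol permits the long gap but does not require it.
- **Section 9 might be read as contradicting Section 5**, because it says "An IRB approved AE Tracking log will be administered by the RA and reviewed by the PI at the clinical assessment visits" without mentioning therapy sessions. It does not say that these are the only occasions. It repeats the RA half of the rule and omits the therapist half, so it is an incomplete restatement and not a conflict.
- **Table 1 has weeks as columns, not visit types**, so on its own it does not exclude the task visits. The Section 5 text is the specific statement.
- **Both arms follow the same schedule**, and no efficacy result depends on it.

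**Conclusion.** The point holds as a low-cost improvement to safety data collection. The AE Form is not scheduled at six separate visits where two of five expected events arise. The gap is clearest for image distress, which has no same-day question at all. For EEG discomfort the defect is narrower: the question is asked, but its answer has no stated route into the AE log.

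The wait to the next AE Form after the post-treatment session is at most 14 days or 70 to 84 days, depending on an order that the protocol leaves open. The frequencies by event type are therefore at risk of under-ascertaining procedure-related events. The illustrative ratios of 0.68 to 0.89 rest on assumed event and capture rates and are not estimates for this trial. Nothing in the documents supports a claim of established under-counting or of bias between arms.

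Separately, the statement that suicidality is monitored at every visit and the Table 1 schedule need to be reconciled for these six visits.

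**What to change.** - Have the RA complete the AE Form at the end of every computer-task and EEG session (baseline, mid-treatment, post-treatment), with the same log and PI review as at other visits.
- State that relevant Post-EEG Questionnaire answers are entered in the AE log.
- Add the six visits to the AE row of Table 1. Have Section 9 refer to the full Section 5 schedule, so that the therapist's part is not lost.
- Reconcile the Section 7 wording on suicidality at each visit with Table 1.

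The cost is a few minutes of RA time at visits that the RA already runs, plus text edits. More minor expected events will be logged, and the report should say that procedure-related events were asked about on the day. With the form at each session, the wait to the first AE question falls to zero days whatever the order of the visits.
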